| 9.2 | AUDITING AND INSPECTING..... | 13 |
| 10 | ETHICAL CONSIDERATIONS | 13 |
| 11 | STUDY FINANCES | 13 |
| 11.1 | FUNDING SOURCE | 13 |
| 11.2 | CONFLICT OF INTEREST | 13 |
| 11.3 | SUBJECT STIPENDS OR PAYMENTS | 13 |
| REFERENCES | | 14 |

List of Abbreviations

CAD/CAM – Computer Aided Design/ Computer Aides Milling

CBCT – Cone Beam Computer Tomography

IV –Intravenous

UNC – University of North Carolina

SOD – School of Dentistry

PI – Primary Investigator

CRF – Case Report Form

PHI – Personal Health Information

Study Summary

| | |
|---------------------------------------|--|
| Title | Fabrication of a Definitive CAD/CAM Titanium Abutment Prior to Guided Surgery: A Pilot Study |
| Protocol Number | IRB#13-2376 |
| Methodology | Randomized trial/cohort with 2 arms (experimental) groups |
| Study Duration | 7 months |
| Study Center(s) | Single Center |
| Objectives | To determine if a custom fabricated, patient specific, CAD/CAM titanium abutment that ideally supports the hard and soft tissues with both esthetics and function can be fabricated prior to guided surgery using computed tomography and diagnostic gypsum models |
| Number of Subjects | 24 |
| Diagnosis and Main Inclusion Criteria | Single edentulous space seeking tooth replacement with dental implant |
| Statistical Methodology | Fisher's Exact test |

1 Introduction

This document is a protocol for a human research study. This study is to be conducted according to US and international standards of Good Clinical Practice (FDA Title 21 part 312 and International Conference on Harmonization guidelines), applicable government regulations and Institutional research policies and procedures.

1.1 Background

Conventional dental implant therapy as described by Branemark and colleagues over 3 decades ago involves 3-6 months of healing prior to functional loading following surgical endosseous dental implant placement (Branemark 1983). In the protocol, the implants are buried under the gingival tissues until full healing is completed. Improved dental implant surface technology and osseointegration potential, along with improved understanding of the biology and mechanics of dental implants has led to loading protocols that involve less time for implant healing prior to functional loading. Commonly for single dental implants, loading is completed at 8 weeks, termed early loading (Bornstein et al. 2005, Cooper et al. 2001).

Although dental implants typically are not loaded with function (occlusion) until 8-12 weeks, immediate provisionalization is a procedure commonly provided in the course of dental implant therapy (Cornelini et al. 2005, Degidi et al. 2006, Drago et al. 2004). This protocol involves placing a provisional restoration on the implant that is out of function during the healing period further reducing the time for a patient to have a fixed tooth in the edentulous area.

Although dental implant therapy is considered the gold standard for tooth replacement therapy in most clinical situations, a common concern among practitioners and patients preventing the application of the procedure is the time involved to completion. Even when provisionalization of the implant is completed immediately, a conventional final impression is needed following healing of the dental implant. The patient is then reappointed for delivery of the final abutment and indirect crown restoration. Depending on the loading protocol, treatment can take as long as 3-5 months to complete.

Using cone beam computed tomography, software is available allowing precise virtual placement of an implant and creation of a milled guide from the plan (D'haese et al. 2010). This milled surgical guide allows the surgeon to place the implant precisely as planned using the patient's CBCT information. Utilizing this virtual plan, it is theoretically possible to fabricate a CAD/CAM patient specific abutment prior to surgery. This allows delivery of the abutment either at surgery or at delivery of the crown following osseointegration. Ultimately, fabrication of the final abutment prior to surgery removes that current necessity of appointing the patient for the final impression. Following surgical implant placement, the next appointment for the patient would be delivery of the final crown. Dental implant therapy could be reduced to 8 weeks of total therapy and 2 total appointments.

While guided surgery for the placement of the implant fixture is extremely precise and is milled from the virtual plan using the patient's CBCT information, surgical guides can have minor error leaving the implant in a position slightly different from the information in the virtual software (Turbush et al. 2012, Sarment et al. 2003). If the abutment and/or crown are produced prior to surgery, these slight differences in the virtual vs. actual position of the implant may provide an abutment and/or crown that either doesn't fit or is esthetically unpleasing.

It is the interest of this study to investigate the possibility of creating a patient specific abutment and provisional crown prior to surgery that is functionally and esthetically pleasing. With this treatment possibility, the time and expense involved with single tooth dental implant therapy will be reduced allowing a better experience for both patient and provider.

1.2 Clinical Data to Date

There is no available clinical data that pertains to this study in which this protocol developed by Astra-Tech is used to fabricate custom Atlantis abutments prior to guided surgery.

2 Study Objectives

Purpose: To evaluate the possibility of fabricating an ideal CAD/CAM custom abutment that adequately supports the hard and soft tissues in a single edentulous space prior to guided surgery. Evaluation of the custom abutment will be completed at 2 intervals post operatively, with abutment exposure being the primary outcome at follow-up. With knowledge of fabricating the definitive CAD/CAM abutment prior to surgery, soft tissue development can begin immediately and restoration of the implant can be completed without subsequent soft tissue trauma during crown fabrication.

Participants: The study will seek 24 patients with a minimum of 20 teeth who have a bound edentulous space who seek restoration with a dental implant crown.

Procedures (methods): This is a convenience sample, we will recruit subjects who present to the graduate prosthodontics clinic or inquire about the study will be eligible to receive dental implant surgery with subsequent definitive abutment and provisional crown delivery at eight weeks. The group will then be randomly split with half of the group receiving a custom abutment with margin placement .5mm sub-gingivally and half of the group receiving a custom abutment with margin placement 1.5 mm sub-gingivally. Final impression for the definitive e-max all-ceramic crown will be completed at eight weeks with final crown delivery at eleven weeks. Follow-up and data collection will be completed at eight weeks, eleven weeks, and twenty-four weeks post operatively.

Primary Objective

Abutment margin exposure

Secondary Objective

Provisional crown fit.

3 Study Design

3.1 General Design

The general design of the study is a cohort study with 2 arms in which subjects are randomly assigned to one of 2 experimental groups. The expected duration of subject participation is 7 months. The subjects will complete 7 appointments within this 7 months span that includes initial screening, CBCT evaluation of the site, surgical placement of the dental implant, restoration of the dental implant and associated follow-ups at 7 days, 8 weeks, 11 weeks and 24 weeks.

3.2 Primary Study Endpoints

The primary objective is to compare differences in margin exposure of the abutment between baseline to 6 months later.

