6.2 Statistical Methods

Demographics and other baseline characteristics will be presented by means of descriptive statistics.

The primary objective is to compare differences in margin exposure of the abutment between baseline to 6 months later. The null hypothesis is that there is no difference in the margin exposure of the abutment between those 2 visits. Ho will be tested by means of Fisher's exact test, after each abutment margin is classified as it shows or not. A p-value less than 5% will be regarded statistically significant.

Secondary objectives include:

Measurement of the soft tissue response based on the condition of the peri-implant mucosa (bleeding on probing). Fisher's exact test will be used after the site has been evaluated for presence of bleeding or not. Provisional crown fit at delivery of provisional crown- Fisher's exact test will be used after the provisional crown is determined to fit or not.

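### The primary test compares margin exposure between an undefined baseline and 6 months; on the only baseline that can be scored, an abutment exposed from delivery onward counts the same as one never exposed

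*Combined protocol and SAP*

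**What the plan says.** The Study Summary gives the objective as learning whether a patient-specific abutment that supports hard and soft tissue well "can be fabricated prior to guided surgery using computed tomography and diagnostic gypsum models". Section 1.1 names the risk: "slight differences in the virtual vs. actual position of the implant may provide an abutment and/or crown" that fits badly or looks poor.

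The primary outcome is worded in two ways.

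- **As a status.** Section 2 names abutment margin exposure as the primary objective and describes exposure at follow-up as the primary outcome.
- **As a contrast between visits.** Section 3.2 says: "The primary objective is to compare differences in margin exposure of the abutment between baseline to 6 months later". Section 6.2 repeats this and adds: "The null hypothesis is that there is no difference in the margin exposure of the abutment between those 2 visits". The test follows: "Ho will be tested by means of Fisher's exact test, after each abutment margin is classified as it shows or not".

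Only the second wording has a hypothesis and a test. Neither section says which visit is baseline.

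On timing, section 5.3 leaves the implant under a cover screw after surgery. Sections 2 and 5.5 place abutment and provisional crown delivery at week 8. Exposure is recorded at weeks 8, 11 and 24 (sections 5.5 to 5.7). Provisional crown fit at delivery is a secondary outcome (sections 3.3 and 6.2).

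**The concern.** The failure described in section 1.1 is fixed when the implant is placed and can first be seen when the pre-made abutment is seated. If baseline is that same visit, the comparison starts after the failure has occurred. It then registers only what changes later, such as tissue receding from a margin or growing over it.

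Three things follow.

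- The primary test can show no difference whatever the exposure rate at delivery, so it does not tell a good set of abutments from a poor one.
- Subjects already exposed at week 8 cannot become newly exposed, so frequent failure at delivery leaves fewer subjects in whom worsening can be seen.
- If tissue later covers a margin exposed at delivery, the change is in the favourable direction.

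Section 1.2 says there are no clinical data on this procedure, so the primary result would be the first evidence on it.

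**Working it through.** The plan has no power calculation or exposure rate to reproduce; section 6.1 sets the sample size on feasibility. All exposure counts below are therefore assumptions.

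**Inputs from the documents**

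- Total of 24 subjects (section 2: "The study will seek 24 patients with a minimum of 20 teeth").
- Two equal arms, so 24 / 2 = 12 per arm, with margins 0.5 mm or 1.5 mm below the gingiva (section 2: "half of the group receiving a custom abutment with margin placement 1.5 mm sub-gingivally").
- Binary outcome and Fisher's exact test (section 6.2).
- Significance level: "A p-value less than 5% will be regarded statistically significant". Sidedness is not stated; two-sided is assumed.

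**Step 1: which visit can be baseline.** At surgery there is a cover screw and no abutment, so no margin can be classified as showing or not. The week 1 visit is a healing check with no abutment in place. Week 8 is the first visit with an abutment. Section 6.2 speaks of two visits, so the only pair with a scorable baseline and a 6-month reading is week 8 and week 24.

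**Step 2: what the contrast does with persistent exposure.** Let x of 24 margins show at both visits, with no other change. The visit difference is x/24 − x/24 = 0 for every x. The proportion unexposed at delivery is (24 − x)/24.

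| x exposed at both visits | Unexposed at delivery | Visit difference | Fisher p, 24 vs 24 |
|---|---|---|---|
| 0 | 100% | 0 | 1.0 |
| 8 | 67% | 0 | 1.0 |
| 12 | 50% | 0 | 1.0 |
| 24 | 0% | 0 | 1.0 |

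A paired test does not help: there are no discordant pairs, so exact McNemar also shows no change.

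**Step 3: what the test does react to.** It responds only to net change after delivery. The fewest new exposures that reach p < 0.05, with none resolving, are:

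| Exposed at week 8 | Still able to become exposed | New exposures needed | Fisher p |
|---|---|---|---|
| 0 | 24 | 5 | 0.0496 |
| 8 | 16 | 8 | 0.042 |
| 12 | 12 | 8 | 0.030 |
| 20 | 4 | not reachable (all 4 give 0.109) | – |

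**Step 4: the same data as a status.** The proportion exposed, with its Clopper-Pearson 95% CI, separates the cases that step 2 could not:

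- 0/24 = 0% (0% to 14.2%)
- 12/24 = 50% (29.1% to 70.9%)
- 24/24 = 100% (85.8% to 100%)

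Between arms, suppose 6/12 against 0/12 are exposed at delivery and remain so. Fisher's test on status gives p = 0.014. On change since delivery the same subjects give 0/12 against 0/12, p = 1.0.

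**The case against.** **Baseline might be surgery.** Section 5.7 dates the last visit as 6 months after surgery, and week 8 to week 24 is only 24 − 8 = 16 weeks. If every margin were taken as unexposed at surgery because it was designed below the gingiva, persistent exposure would count: 0/24 against 8/24 gives p = 0.004. This objection stands so far as to make week 8 an inference and not a stated fact. But there is no margin to classify at surgery, the documents nowhere assign a value of zero, and a margin exposed at week 8 and covered by week 24 would still be missed. Sections 3.2 and 6.2 would need rewriting on this reading too.

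**Section 2 already words the outcome as a status.** True, and on that wording an abutment still exposed at follow-up is a failure. But no null, estimate or test is attached to it, so the three sections conflict.

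**Delivery failure is partly covered.** This also stands. Exposure is recorded at week 8, and provisional crown fit is tested as a secondary outcome. But crown fit is a different variable, since a crown can fit while the margin shows, and no analysis of week 8 exposure is planned.

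**Later tissue change is relevant.** Agreed: the objective includes soft-tissue support, and margin depth is the randomised factor. That is a reason to keep the change as a secondary outcome.

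**Stronger readings to avoid.** A reader might infer that the outcome variable itself discards delivery failures, or that the plan treats a non-significant result as success. The documents support neither. Each margin is classified as a status and the readings are kept; it is the contrast between visits that cancels them. Nothing in section 6.2 gives a success rule for a non-significant result.

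**Conclusion.** The concern holds as a mismatch between the question asked and the only primary hypothesis tested, together with an undefined baseline and conflicting wording in sections 2, 3.2 and 6.2. With delivery as baseline, any number of margins from 0 to 24 exposed at both visits gives the same primary result, p = 1.0. The loss is from the primary analysis, not from the data collected.

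This rests on one inference, that baseline is week 8, which follows from the visit schedule but is not stated. How much it would matter in practice cannot be sized, because the documents give no expected exposure rate; the counts used here only show how the test behaves.

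**What to change.** 1. **Sections 2, 3.2 and 6.2:** use one primary outcome throughout, exposure status per subject (margin shows, yes or no). One workable definition is exposed at any of weeks 8, 11 or 24. Show status at each visit alongside it, so that transient exposure is visible, and state how a missed visit is handled.
2. **Section 6.2:** replace the visit-versus-visit null with the proportion exposed and its exact 95% CI, plus a Fisher's exact comparison of that status between the two margin-depth arms.
3. **Sections 3.2 and 6.2:** define baseline as week 8 (delivery). Keep the week 8 to week 24 change as a secondary outcome describing later tissue movement, analysed as paired data (for example exact McNemar), because the same subjects are seen at both visits.

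**Cost:** wording only; no added visits, readings or patients. The headline figure may be less favourable than a change score, and an any-visit definition counts exposure that later resolves. With 12 per arm the comparison between arms detects only large differences: 5/12 against 0/12 gives p = 0.037, while 4/12 against 0/12 gives p = 0.093. The proportion and its interval should therefore carry most of the interpretation.

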3.3 Secondary Study Endpoints

Secondary Objectives include measurement of the soft tissue response based on the condition of the peri-implant mucosa (bleeding on probing) as well as provisional crown fit.

4 Subject Selection and Withdrawal

4.1 Inclusion Criteria

1. Partially edentulous with single edentulous space seeking dental implant tooth replacement therapy
2. Age 18-99
3. Edentulous site where previous tooth has been extracted for at least 2 months

4. Minimum of 20 teeth present in mouth
5. Consent to Participate in Clinical Trial
6. Able to tolerate dental implant surgical and restorative procedures

4.2 Exclusion Criteria

1. ASA Class 3+, Immunocompromised, Contraindicated for dental implant therapy in the UNC Department of Prosthodontics

2. Present drug abuse, Pregnant or plans to be pregnant at any point during trial

3. Patients in need of lateral window sinus graft

4. Patients in need of grafting prior to implant placement

5. Patients in need of extensive grafting at time of implant placement

6. Tooth is present or extracted within the last 2 months

7. History of IV bisphosphonate use or oral bisphosphonate use contraindicating dental implant therapy

8. Untreated caries or periodontal disease

9. Severe bruxism

10. Smoker within the past 6 months

11. Unlikely to be able to comply with the study procedures according to investigators

12. Known allergy to any materials used in dental implant surgery

4.3 Subject Recruitment and Screening

Patient will be identified by 2 methods. Patients will self-identify themselves for the study if they are interested in participation via response to mass-email and website inquiries. Patient will also be identified and inquired about possible inclusion in the study if they present to the school of dentistry with qualifying inclusion criteria.

Patients will be recruited through e-mail correspondence and advertisement on the UNC Department of Prosthodontics website. Patients will also be recruited in person if patients present with qualifying inclusion criteria. It is the belief of the primary investigator that no problems will be encountered in recruiting the allotted number of patients to complete the study. Inquiries about the study will be answered and the investigators only will conduct enrollment in the study. Subjects will be contacted during the study by telephone or direct mail.

4.3.1 When and How to Withdraw Subjects

Subjects may withdraw at any point during study. There are no circumstances for discontinuation unless CBCT reveals that a dental implant is not possible in the site or a subject becomes pregnant during the study period.

4.3.2 Data Collection and Follow-up for Withdrawn Subjects

Even though subjects may be withdrawn prematurely from the study, it is imperative to collect at least survival data on such subjects throughout the protocol defined follow-up period for that subject (though careful thought should be given to the full data set that should be collected on such subjects to fully support the analysis). If a subject withdraws consent to participate in the study, attempts will be made to obtain permission to record at least survival data up to the protocol-described end of subject follow-up period.

4.4 Method for Assigning Subjects to Treatment Groups

Subjects will be assigned to treatment groups through randomization methods.

4.5 Preparation and Administration of Study Drug

N/A

4.6 Subject Compliance Monitoring

N/A

4.7 Prior and Concomitant Therapy

N/A

4.8 Blinding of Study Drug (if applicable)

N/A

4.9 Receiving, Storage, Dispensing and Return

4.9.1 Receipt of Drug Supplies

An IIS is submitted to AstraTech and supplies for study will be supplied by the company that include implant surgical supplies, implants, and impression copings, among other items needed to conduct protocol.

Upon receipt of the study treatment supplies, an inventory must be performed and a drug receipt log filled out and signed by the person accepting the shipment. It is important that the designated study staff counts and verifies that the shipment contains all the items noted in the shipment inventory. Any damaged or unusable study drug in a given shipment (active drug or comparator) will be documented in the study files. The investigator must notify study sponsor of any damaged or unusable study treatments that were supplied to the investigator's site.

4.9.2 Storage

N/A

4.9.3 Dispensing of Study Drug

N/A

4.9.4 Return or Destruction of Study Drug

N/A.

5 Study Procedures

5.1 Visit 1 (1 hour)

Appointment 1: Screening Exam (1 hour), Prior to inclusion into study

All patients will receive standard care for their initial clinical appointment. This appointment is not research-driven. Standard care includes:

- General extraoral and intraoral exam
- Maxillary and mandibular alginate impressions
- Standardized radiographs (panoramic film)
- Standardized photographs
- Completion of the dental implant surgery consent form
- Completion of the treatment in the graduate Prosthodontic clinic consent form

If the patient is eligible for the research study, s/he will be introduced to the study and given a copy of the consent form to take home. If the potential subject is interested in participating in the study, the consent form will be signed at the beginning of visit 2 and the subject will be enrolled.

5.2 Visit 2

Appointment 2: Completion of consent for inclusion into study, CBCT with scanning appliance

CBCT will be obtained of surgical site to be used for planning and surgical guide fabrication. This procedure is the standard of care for implant patients within the school of dentistry.

5.3 Visit 3

Appointment 3: Place implant in healed alveolar ridge

Each patient will have the opportunity to ask remaining questions about the surgery protocol. Each patient will use a pre-operative rinse of antibacterial mouth rinse (Peridex).

Standard UNC Graduate Prosthodontics clinic protocol for implant placement will be used including full body sterile drape of patient as well as surgical scrub of both operator and assistant. Local anesthetic will be used at

surgical site (2% lidocaine 1:100,000 Epinephrine).

An Astra Tech dental implant will be placed using standard clinical protocol. The dental implant will be covered with a cover screw to allow soft tissue healing. A post-operative radiograph will be made to demonstrate proper placement of the implant in bone.

The patient will be prescribed normal post-operative medications including analgesics and anti-bacterial mouth rinse (peridex). All procedures listed are the standard of care for implant placement.

5.4 Visit 4

Appointment 4: Follow-up (1 week post-op)

Usual and customary follow-up to be completed to verify adequate and acceptable healing of surgical site. This procedure is the standard of care for implant placement.

5.5 Visit 5

Appointment 5: Final impression (8 weeks post-op) for full coverage crown

Final impression for crown fabrication of the abutment will be completed at 8 weeks post surgery using standard clinical protocol. Provisional restorations will be placed onto final abutments delivered at same appointment. These procedures are standard of care for all participants. Research-driven data to include abutment exposure will be collected from subjects regarding fit of the provisional restoration. A peri-apical radiograph of the implant in bone is produced to demonstrate the proper connection of the abutment to the implant at the time of placement of the abutment.

5.6 Visit 6

Appointment 6: Delivery final E-max crown restoration (11 weeks post-op)

Delivery of final crown will be completed using standard clinical protocol at 11 weeks post-surgery. Research driven data to include abutment exposure will be collected from all subjects regarding esthetics of the final abutment.

5.7 Visit 7

Appointment 7: Follow-up 24 weeks post-op

Follow-up of crown restorations will be completed at 6 months post surgery (24 weeks). Research driven data to include abutment exposure will be collected for all subjects. Bleeding on probing measurements will be made to evaluate soft tissue health around the abutments (Standard of Care). A peri-apical radiograph will be made for hard tissue evaluation of the abutment (Standard of Care). Photographs will be taken of restorations per standard protocol (photographs are standard of care). The patient will then be dismissed from the study.

6 Statistical Plan

